Protein restriction is a basic but important life intervention to improve the prognosis of DKD patients. How to calculate DPI in a simple and effective way to overcome the complexities and errors of existing methods attracts our attentions. In this study, we hypothesize sUCR can be applied to evaluate of protein intake during the follow-up periods and predict the survival in patients with DKD.

Object

To evaluate the prognostic value of sUCR in the progression of DKD.

Methods

This study is a multicenter, retrospective cohort study. We select patients diagnosed with DKD since January 2012. The present study is performed according to the principles of the Declaration of Helsinki and has been approved by the Ethics Committee of Guangdong Provincial People's Hospital.

Study population

We screen DKD patients aged 18-70 years with CKD stages 1-4. DKD was defined as those diagnosed by pathological biopsy, or those with eGFR <60 ml/min per 1.73 m², or presence of clinically detectable albuminuria over 3 months which is caused by diabetes. Patients who undergo infection, severe liver disease, malignant tumor, acute heart failure, gastrointestinal hemorrhage, pregnancy are excluded.

Data collection

At baseline and every medical visit, therapeutic relevant information will be collected. Data mainly include demographic characteristics (age, gender, place of residence, marriage status, education degree), lifestyle (smoking, drinking, exercise), clinical characteristics (body mass index, blood pressure, duration, history of CVD, complications, nutrition situation), laboratory indexes (serum creatinine, blood urea nitrogen, glycosylated hemoglobin, urinary albumin to creatinine ratio, 24-hour urinary albumin, 24-hour urine urea nitrogen, etc.). History of cardiovascular disease including coronary artery disease, congestive heart failure, stroke, and peripheral vascular disease were ascertained by self-report or doctor's diagnosis.

Outcomes

Patients are followed for survival until they reach the end of the study, whichever happen first, or are censored because they lose contact or the follow-up interval is less than one month. The outcomes are all-cause death, a composite of end-stage kidney disease (dialysis, transplantation, or a sustained estimated GFR of <15 ml per minute per 1.73 m², or increasing by 50% of the serum creatinine level from baseline. Evaluated GFR was calculated using Chronic Kidney Disease Epidemiology Collaboration (CKD-EPI) formula.

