Statistics

Data are presented as mean \pm SD for continuous variables and as a number (percentage) for categorical variables. According to mean sUCR and Δ sUCR (fluctuation of sUCR over time, meaning monthly rate of change), patients are divided into four groups. The relationship between baseline characteristics among the four groups was compared by using one-way analysis of variance test, Kruskal-Wallis test or Chi-squared test where appropriate. Survival rates are estimated using Kaplan Meier analysis, and the significance of differences are analyzed using the log-rank test. Cox proportional hazard regression analysis is used to assess the association between the clinical outcomes and mean sUCR and Δ sUCR. In multivariate analysis, we enter variables using a P value of <0.10 as the selection criterion or considered clinically significant. Hazard ratios (HRs) are presented with 95% CIs. All statistical analysis was performed with the use of SPSS (version 19.0, SPSS, Chicago, USA) and Prism 7.0 (GraphPad Software, San Diego, CA, USA). A two-tailed P value <0.05 was considered to be statistically significant.

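### The 50% creatinine rise needs no confirmation, *sustained* eGFR is undefined, and sUCR is not limited to pre-event values; the bias is of unknown direction and size

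*Combined protocol and SAP*

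**What the plan says.** - **Kidney outcome (Outcomes).** Dialysis and transplantation are listed with two laboratory criteria. One is "a sustained estimated GFR of <15 ml per minute" (per 1.73 m²), with no duration or number of values to define *sustained*. The other is "or increasing by 50% of the serum creatinine level from baseline", with no repeat value, minimum interval or handling of acute reversible rises.
- **Source of the values (Methods, Data collection).** "This study is a multicenter, retrospective cohort study", and "At baseline and every medical visit, therapeutic relevant information will be collected". No visit interval or number of visits is stated.
- **Follow-up (Outcomes).** The only rule on length is censoring when "the follow-up interval is less than one month".
- **Exposure and model (Statistics).** Patients are grouped by mean sUCR and by ΔsUCR, described as "fluctuation of sUCR over time, meaning monthly rate of change". Cox regression is "used to assess the association between the clinical outcomes and mean sUCR" and ΔsUCR. The section does not say which values enter the mean or the rate of change, or that they must precede the event. It adds no event rule.

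**The concern.** The stated object is the prognostic value of sUCR for progression of DKD, and a creatinine rise that later reverses is not progression. Within one sentence the plan asks for persistence in one laboratory criterion and not in the other. Someone deriving events from the records could therefore count an isolated high creatinine and still be following the text.

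The second gap is linked but distinct. A 50% rise in creatinine changes sUCR at the same visit unless urea rises by the same factor. If that visit is included in the mean or the rate of change, the outcome has helped to set the exposure. A hazard ratio from such a model is not evidence that sUCR predicted anything.

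**Working it through.** The documents state no sample size, event count, effect size, visit schedule or creatinine variability, so there is no plan figure to reproduce. Every rate below is an assumption, chosen to show direction and range.

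**1. How the event value moves the exposure.** If creatinine rises by 1.5 and urea by a factor *u*, sUCR at that visit is multiplied by *u*/1.5. This is 0.67 for *u* = 1, 1.00 for *u* = 1.5 and 1.33 for *u* = 2. Take four values, otherwise constant, with the event value last. The mean becomes (3 + 0.67)/4 = 0.92 or (3 + 1.33)/4 = 1.08 of its former level, so the shift can go either way.

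**2. No true association.** Simulation: 40 data sets of 4,000 patients, baseline plus 12 visits, 1.5% true events and 1% transient rises per visit. Log sUCR has SD 0.25 between and 0.15 within patients. Mean sUCR is split at the median and a Cox model fitted. Transient rises are unrelated to sUCR, and there is no death or loss to follow-up. Hazard ratios for *u* = 1.0 / 1.5 / 2.0:

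| Values used for mean sUCR | Single value counts | Next visit must confirm |
|---|---|---|
| Through the event | 0.69 / 1.00 / 1.40 | 0.67 / 1.00 / 1.40 |
| Before the event only | 1.00 / 1.00 / 1.00 | 1.00 / 0.99 / 0.97 |

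The Monte Carlo standard error of the log hazard ratio is 0.01 to 0.02. In a separate run of 15 data sets, ΔsUCR through the event gave 0.10 / 1.00 / 6.31 with a single value and 0.09 / 0.99 / 6.68 with confirmation. With pre-event values it gave 0.96 to 1.03 under either rule.

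**3. True association present.** Same set-up, 10 data sets, hazard ratio about 1.47 with no false events. With sUCR through the event and a single-value rule, the estimate is 0.85 / 1.27 / 1.78: reversed, diluted or exaggerated.

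**4. Pre-event exposure, transient rises unrelated to sUCR.** Let true event rates be 1.2% (low sUCR) and 1.8% (high sUCR) per visit, so the true hazard ratio is 1.5 and the mean rate 1.5%. Add a transient rate *b* to both groups. Observed hazard ratio = (1.8 + *b*)/(1.2 + *b*); share of counted events that are false = *b*/(1.5 + *b*).

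| *b* (% per visit) | Observed hazard ratio | False share |
|---|---|---|
| 0.1 | 1.46 | 6% |
| 0.25 | 1.41 | 14% |
| 0.5 | 1.35 | 25% |
| 1 | 1.27 | 40% |
| 2 | 1.19 | 57% |

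**5. Pre-event exposure, transient rises related to sUCR.** With no true association and an assumed 1.35-fold transient rate per SD of sUCR, the single-value rule gives a hazard ratio of about 1.2, and confirmation brings it back to about 1.0. Here the missing rule alone creates an association.

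**6. A different set-up.** Simulation: 16,000 patients, 12 visits three months apart, 2% transient rises per visit, no true association. With a single value, the hazard ratio per SD of mean sUCR was 0.90, 0.99 or 1.09 as urea rose not at all, in proportion, or more than creatinine. Two values brought it to 0.99 to 1.03. ΔsUCR stayed at 0.71 to 0.82 even with two values. How much each gap contributes therefore depends on the assumptions, but confirmation did not free ΔsUCR from the coupling.

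**The case against.** **The text does not say that one value is enough.** True. The plan is silent and the investigators may intend a repeat. But an analyst working from the text has nothing to apply, and the contrast with the eGFR criterion invites the single-value reading.

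**A reader might infer that one isolated eGFR below 15 also counts.** The documents do not support that: *sustained* on its face excludes it. What is missing there is the definition.

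**A reader might infer that the effect is simply dilution, and so conservative.** That needs pre-event exposure and transient rises unrelated to sUCR. The plan states neither. Nor can any either-way bias be put down to the exposure window alone, as step 5 shows.

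**A reader might infer bias from visit frequency.** At an assumed 1% transient rate per visit, 1 − 0.99^n gives 3.9%, 11.4% and 21.4% of patients with at least one transient value in 4, 12 and 24 visits. More visits over a longer time is ordinary time at risk. It biases the comparison only if visit intensity is related to sUCR, and the documents do not say whether it is.

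**The effect may be small.** The Study population section excludes patients with infection, acute heart failure and gastrointestinal hemorrhage. If this applies during follow-up, it removes some causes of acute rises, and the low end of step 4 (1.5 becoming 1.46) is possible. The timing of these exclusions is unstated, and they would not touch the exposure-window problem. This objection limits the size that can be claimed and leaves the gap open.

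**Conclusion.** The concern holds as two gaps. The creatinine criterion has no confirmation rule and *sustained* is undefined; and exposure is not limited to pre-event values although creatinine sits in both exposure and outcome. Followed as written, the plan can count reversible rises as progression and let the event value set the exposure. The hazard ratio may then be diluted, exaggerated, reversed or created.

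The omissions are certain from the text. Direction and size are not: they depend on how urea moves with creatinine, how common transient rises are and whether they relate to sUCR, and the documents give none of these. The figures are illustrations under assumed rates. The detailed simulations in steps 2 and 3 also assume equal visit counts and no death. Confirmation alone does not remove the coupling, so both rules are needed. The plan should be changed before events and exposures are derived.

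**What to change.** **Confirmation.** Prespecify one rule for both laboratory criteria (eGFR below 15, creatinine at least 1.5 times baseline): a second qualifying value at least a fixed interval later, or dialysis or transplantation before a second value. The 3 months in the DKD definition ("presence of clinically detectable albuminuria over 3 months") would be one consistent choice. State how death before a second value is handled, for example counted under all-cause death with the kidney criterion unconfirmed. Date the event at the first qualifying value, and report the unconfirmed definition as a sensitivity analysis.

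**Exposure.** Compute mean sUCR and ΔsUCR only from values before the event, leaving out the values that define it. Use either a lagged time-updated exposure or a landmark at which the clock starts. The lagged form keeps sUCR during follow-up, which is what the Background hypothesises. A landmark, if used, should be early. Count and report patients without the two values that ΔsUCR needs.

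**Cost.** SAP wording, and re-derivation from creatinine and urea values already collected. Some true events are lost. At an assumed 1.5% per visit over *n* visits:

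- *No later value.* If the next visit must confirm, the share falling at the last visit is 0.985^(n−1) × 0.015/(1 − 0.985^n): 24%, 8% and 3% for 4, 12 and 24 visits. A longer interval loses more when visits are close together. With a 3-month interval, patients followed for 1 to 3 months could not be confirmed by a second value.
- *No pre-event ΔsUCR.* The share falling at the first follow-up visit is 0.015/(1 − 0.985^n): 26%, 9% and 5%.
- *Landmark at visit k.* All earlier events, including those at visit k, drop out: (1 − 0.985^k)/(1 − 0.985^n). With 12 visits this is 18%, 35% or 52% for k = 2, 4 or 6; with 4 visits and k = 2 it is 51%.

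### Mean sUCR and ΔsUCR have no exposure window and time zero is undefined; if all follow-up visits define them, later values are treated as known at the start

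*Combined protocol and SAP*

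**What the plan says.** The Object section sets the aim: "To evaluate the prognostic value of sUCR in the progression of DKD". The hypothesis that closes the Background reads: "we hypothesize sUCR can be applied to evaluate of protein intake during the follow-up periods and predict the survival in patients with DKD". Methods describes the design: "This study is a multicenter, retrospective cohort study. We select patients diagnosed with DKD since January 2012". Under Data collection, "At baseline and every medical visit, therapeutic relevant information will be collected".

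The Statistics section defines the exposure: "According to mean sUCR and Δ sUCR (fluctuation of sUCR over time, meaning monthly rate of change), patients are divided into four groups". It continues: "Survival rates are estimated using Kaplan Meier analysis, and the significance of differences are analyzed using the log-rank test". For regression, "Cox proportional hazard regression analysis is used to assess the association between the clinical outcomes and mean sUCR and Δ sUCR".

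The word baseline appears in Data collection, in Outcomes and in Statistics, but no section says which date it is or that the survival clock starts there. The plan also does not state:

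- which visits or months feed the mean and the rate of change;
- how many values a patient needs;
- where the four groups are cut;
- whether ΔsUCR is signed or absolute;
- whether it enters Cox as continuous or grouped;
- whether a landmark or time-dependent covariate is used.

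Outcomes treats patients with under one month of follow-up as censored. That is the only rule bearing on very short follow-up.

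**The concern.** A rate of change needs at least two dated values, so it cannot be known at a single baseline visit. Values come from every visit and the hypothesis concerns the follow-up period. The natural reading is therefore that mean sUCR and ΔsUCR summarise the same follow-up in which events are counted.

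On that reading each patient carries from time zero a value that could be computed only later, and whose precision depends on how long the patient was followed. A patient who dies early has few visits and so a noisy, often extreme slope. If sUCR drifts, the mean also depends on length of follow-up. A quantity that needs later visits cannot predict from time zero, and prognosis is the aim. These are the only outcome analyses in the plan, so no other analysis would reveal the problem.

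**Working it through.** The plan gives no sample size, event count, visit spacing or sUCR variability, so there is no figure of its own to reproduce. Every input below is an assumption, apart from the two-sided 0.05 level.

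**Step 1: mechanism for ΔsUCR.** The noise in a least-squares slope has SD = σ / √Σ(tᵢ − t̄)². Take visit noise σ = 0.15 on the log scale and 3-monthly visits.
- Two values (months 0 and 3): Σ = 2 × 1.5² = 4.5, so SD = 0.15/√4.5 = 0.071, or about 7.1% per month.
- Thirteen values (months 0 to 36): Σ = 9 × 13 × (13² − 1)/12 = 1,638, so SD = 0.15/√1,638 = 0.0037, or about 0.37% per month.

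The short record is about 19 times noisier. A few early deaths with extreme slopes can then drive the Cox coefficient. If the slope is signed, its direction is chance. If it is absolute, the errors all point the same way.

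**Step 2: mechanism for mean sUCR.** With drift d per month, the average over follow-up L shifts by d × L/2. At d = −0.005 (log scale) the shift is −0.015 for L = 6 and −0.150 for L = 60. The difference of 0.135 is 0.54 of a between-patient SD of 0.25. Patients followed briefly then appear to have high sUCR.

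**Step 3: null simulation.** Death is unrelated to sUCR. Inputs: n = 500; death 5% per year; censoring uniform over 6-60 months; visits every 3 or 6 months; between-patient log SD 0.25; visit noise 0.15; drift 0 or −0.5% per month; patient slope SD 0 or 0.5% per month; patients with one value omitted. There were 8 scenarios of 1,000 runs, plus sensitivity runs.

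| Whole follow-up defines the exposure | Share with P<0.05, and HR |
|---|---|
| Signed ΔsUCR, continuous in Cox | about 30-55%; average HR near 1; 5th-95th percentile about 0.5-2.0 per SD with regular visits |
| Signed ΔsUCR, ranks | about 15-20% |
| Signed ΔsUCR, median split | 5-7%; HR 0.97-1.03 |
| Absolute ΔsUCR, continuous | HR about 1.8-2.0 per SD; mostly significant with regular visits |
| High v low mean sUCR, no drift | HR 0.97-1.01 |
| High v low mean sUCR, −0.5%/month | HR about 1.3; 12-18% |
| High v low mean sUCR, +0.5%/month | HR 0.76; 19% |
| 2×2 median groups, log-rank, no drift | 6-10% |
| 2×2 median groups, log-rank, −0.5%/month | 11-20% |
| 2×2 median groups, log-rank, patient slope SD 1%/month (stress case) | 26% |

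**Step 4: sensitivity.** Requiring three values (45%), or first and last values 3 months apart (38-45%), does not cure continuous ΔsUCR. A second model (n = 600, events 10% per year, censoring 6-96 months, sUCR mean 15, between-patient SD 4, visit SD 3) gave 41-58%, and absolute change gave HR 2.2-3.2. Runs with one covariate at a time reached 62-65% with 3-monthly visits.

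**Step 5: after the fix.** With regular visits, a 6- or 12-month landmark brings the tests to about 4-7%, and time-dependent Cox gives 4-7%. With irregular visits, the 12-month landmark gives 7-10% for continuous ΔsUCR if two values at any spacing suffice, and 5-6% if first and last values are at least 3 months apart. Time-dependent Cox gives 4-8%.

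**The case against.** The best case for the plan has four parts.

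First, nothing says that all follow-up visits are used, and the authors may have a fixed window in mind. This stands as a caution. A reader might infer that the plan prescribes exposures measured after time zero; it does not say so. What is documented is the omission, and the exposure cannot be reproduced from the text whichever window was meant.

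Second, the high false-positive rates need ΔsUCR to enter Cox as a continuous slope from as few as two values. The only coding the plan describes is four groups, and median groups without drift are barely affected. This stands too. A reader might infer that the four-group comparison is invalid whatever the data; that is not supported without drift or widely differing patient slopes.

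Third, it is tempting to say that the hazard ratio for ΔsUCR is biased. For a signed slope unrelated to the event, the average stays near 1, so the defect is false positives and instability. Directional bias arises if *fluctuation* means absolute change, or if late values track the outcome. In the second model, lowering the last value before an event by 10% gave HR 0.50-0.57 per SD.

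Fourth, a baseline is named, and follow-up under one month is handled. Both are true. But the baseline is undefined, and the one-month rule does not secure enough spaced values, given that stricter rules failed in Step 4.

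**Conclusion.** The point holds in conditional form. The plan does not define time zero and sets no window, landmark or time-dependent covariate for its two exposures. If all follow-up visits define them, which is the natural reading, the analyses use later values as if known at time zero and cannot show prognostic value.

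How far the P values and hazard ratios suffer depends on choices that the plan leaves open. Harm is severe for continuous ΔsUCR and for absolute change, moderate for ranks, and negligible for a median split. For mean sUCR and the four-group log-rank it is material only with drift or widely differing slopes.

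The percentages are illustrative and cover death only. They rest on the assumed visit pattern, event rate, variability and censoring. In particular, no one is censored before month 6 in the main runs; earlier censoring would give some censored patients noisy slopes too and could change the size. The omission itself rests on no assumption and should be settled before outcomes are examined by sUCR.

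**What to change.** - Define time zero.
- State that ΔsUCR is a signed least-squares slope per month or, if absolute change is meant, say so.
- Compute mean and slope only from a fixed window after baseline, 6 or 12 months, chosen from the follow-up distribution before looking at outcomes by sUCR.
- Require at least two values and a minimum gap between first and last, for example 3 months, because visits are those of routine care.
- Start risk time at the end of the window in patients event-free and under follow-up, and report how many are lost before it.
- Use this landmark for Kaplan-Meier, log-rank and Cox, and state the four-group cut, for example 2×2 at the medians.
- For Cox only, the running mean and slope up to each visit may instead be time-dependent covariates. This does not replace the landmark for the four-group comparison.
- State as a limitation that sUCR shares creatinine with the renal outcomes, one of which is "increasing by 50% of the serum creatinine level from baseline". With urea constant, such a rise lowers sUCR by 1 − 1/1.5 = 33%. Neither option removes this link.

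**Cost.** Wording and programming, no new data, fewer events, and conclusions limited to patients who reach the landmark. Under the assumed inputs there are 63 deaths, but a whole-follow-up slope analysis that drops single-value patients keeps only 57 (3-monthly visits) or about 50-51 (6-monthly). Those are the fair comparators. The detectable HR for a median split at 80% power is exp(2.8016/√(deaths × 0.25)).

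| Analysis | Deaths | Detectable HR |
|---|---|---|
| Whole follow-up, 3-monthly | 57 | 2.10 |
| Whole follow-up, 6-monthly | about 51 | 2.19 |
| 6-month landmark | about 51 | 2.19 |
| 12-month landmark | about 40 | 2.43 |

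The 12-month landmark loses (57 − 40)/57 = 30%, or 20-22% against 50-51. The 6-month one loses (57 − 51)/57 = 11%, or essentially none. Time-dependent Cox loses essentially none. With irregular visits and the 3-month gap rule, the 12-month landmark keeps about 37 deaths (mean gap 3 months) or 31 (6 months). If follow-up is capped at 24 months, with about 30 deaths in all, it keeps 8, the 6-month landmark 18 and time-dependent Cox 24. The shorter window would then be preferable.

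### If the four groups cross mean sUCR with ΔsUCR and time runs from baseline, patients who die before a second sUCR cannot be grouped, and Kaplan-Meier survival would be overstated

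*Combined protocol and SAP*

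**What the plan says.** The Statistics section forms the exposure groups from two quantities together: "According to mean sUCR and Δ sUCR (fluctuation of sUCR over time, meaning monthly rate of change), patients are divided into four groups". The next analysis steps are "Survival rates are estimated using Kaplan Meier analysis, and the significance of differences are analyzed using the log-rank test" and then "Cox proportional hazard regression analysis is used to assess the association between the clinical outcomes and mean sUCR and Δ sUCR".

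The measurement schedule, under Data collection, is "At baseline and every medical visit, therapeutic relevant information will be collected". No visit interval is given.

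Under Outcomes, follow-up ends at the end of the study, or patients "or are censored because they lose contact or the follow-up interval is less than one month". The kidney outcome there covers dialysis, transplantation, a sustained eGFR below 15, "or increasing by 50% of the serum creatinine level from baseline".

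The plan does not state:
- a minimum number of sUCR values, or what happens to a patient with one;
- the window over which mean sUCR and ΔsUCR are computed;
- time zero for the survival curves, or a landmark;
- the cut-points, and whether the groups cross the two measures or are formed on each separately;
- whether Cox takes the two measures in one model or in two.

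**The concern.** A patient with a single sUCR has a level but no rate of change. Four groups built from two measures most naturally means a two-by-two cross, and in a cross this patient belongs to no cell. These are the only groups defined before the Kaplan-Meier and log-rank sentence, so the patient would be missing from the curves even though the level is known. A Cox model containing ΔsUCR would omit the same patient.

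Getting a second value requires being alive and in contact when it is taken. With time counted from baseline, everyone left on the curve is therefore guaranteed to be alive up to the second test. The patients removed include the earliest deaths, in a study whose title, hypothesis and first-listed outcome concern survival.

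The Outcomes section also treats short follow-up and lost contact as censoring, which means those patients are kept and contribute time. On the crossed reading, the Statistics section gives them no group to contribute to. The two sections need to be made consistent.

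**Working it through.** The documents state no sample size, event count, survival rate or visit gap, so there is no figure of the plan's own to reproduce. All rates and gaps below are assumptions, varied to show a range.

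**Step 1: direction.** Let S(t) be true survival from baseline and t2 the time of the second sUCR. Keeping only patients event-free at t2 while still counting from baseline gives, for t ≥ t2,

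P(T > t | T > t2) = S(t) / S(t2) ≥ S(t).

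This selection can only raise the curve.

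**Step 2: size with a fixed t2.** With constant annual risk r, S(t) = (1 − r)^t, so the curve at 5 years reads (1 − r)^(5 − t2) instead of (1 − r)^5. For example, with r = 5% and t2 = 1 year, 0.95^5 = 77.4% and 0.95^4 = 81.5%, a difference of 4.1 points.

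| Annual risk | True 5-year survival | t2 = 1 month | 3 months | 6 months | 12 months |
|---|---|---|---|---|---|
| 2% | 90.4% | 90.5% | 90.8% | 91.3% | 92.2% |
| 5% | 77.4% | 77.7% | 78.4% | 79.4% | 81.5% |
| 10% | 59.0% | 59.6% | 60.6% | 62.2% | 65.6% |
| 20% | 32.8% | 33.4% | 34.6% | 36.6% | 41.0% |

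From unrounded values, the overstatement runs from 0.2 points (2%, 1 month) to 8.2 points (20%, 12 months).

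**Step 3: which exclusions cause it.** Simulation of 200,000 patients with exponential event times, second sUCR at an exponential time with mean 6 months, and loss of about 10% a year. Kaplan-Meier at 5 years:

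| Analysis set | 5% annual risk | 10% annual risk |
|---|---|---|
| All patients | 77.4% | 59.1% |
| Without a second value, all dropped | 79.3% | 62.2% |
| Only those lost before a second value dropped | 77.3% | 59.0% |
| As row 2, but 60% of events creatinine-defined and so kept | 78.1% | 60.2% |

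Row 2 excludes 7.3% and 9.5% of patients. Row 3 shows that loss unrelated to outcome does not raise survival. With a mean gap of 12 months it lowers it slightly (77.4% to 77.0% at 5% risk). Row 4 shows that the bias shrinks when events carry their own later creatinine.

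**Step 4: events lost, and the hazard ratio.** Simulation of deaths only: 5% a year, hazard ratio 1.5 per SD of sUCR, loss 15% a year, administrative censoring uniform over 0.5–8.4 years, second value at 1 month plus an exponential gap. With mean gaps of 3, 6 and 12 months, about 12%, 19% and 31% of deaths are dropped. Three-year mortality reads 13.2%, 12.4% and 10.6% instead of about 14.8%. The hazard ratio for level stays between 1.48 and 1.52.

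At 2% a year with the other assumptions unchanged, 3-year mortality of 6.3% reads 5.7%, 5.2% and 4.5%. The absolute error is then at most 6.3 − 4.5 = 1.8 points.

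**The case against.** The best case against the point has five parts.

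- **The crossed reading is not written down.** The text also allows four groups on each measure separately, and separate Cox models. One-value patients would then stay in the level analysis. No exclusion or complete-case rule appears anywhere, and that the groups are the sole basis for the curves is inferred from sentence order. This stands, and it makes the point conditional. It does not remove it, because the plan would still have to say which reading applies.
- **Kidney events mostly escape.** A 50% creatinine rise or a sustained low eGFR cannot be recorded without a later creatinine. Data collection lists urea nitrogen alongside creatinine, so a second sUCR usually exists by then. This stands. What remains exposed is death, and dialysis or transplantation before any repeat test.
- **Loss to follow-up does not inflate survival** when it is unrelated to outcome. This stands; such losses cost precision.
- **The size is assumed throughout.** With frequent visits or low mortality it is small. This stands.
- **The objective is prognostic value, assessed by Cox, and the hazard ratio for level hardly moves.** This stands for the hazard ratio. It does not rescue the survival rates the plan also reports, or restore the dropped deaths.

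A reader might go further and infer that every patient who dies, has a kidney event or is lost before a second sUCR is necessarily removed from the level analysis, and that the survival rates are overstated as a matter of fact. The documents do not support that. They contain no exclusion rule, leave the grouping and time zero open, and define two of the kidney criteria by a later creatinine.

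**Conclusion.** The point holds conditionally. It requires that the groups cross mean sUCR and ΔsUCR, that time starts at baseline, and that some deaths (or dialysis or transplantation) come before a second test. Under those conditions the direction of the bias is certain. Its size in this study is unknown, because neither the event rate nor the visit gap is given. The range of about 0.2 to 8 percentage points at 5 years describes the assumed grid of risks and gaps and is not a forecast for this cohort.

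The harm falls on the absolute survival rates and on the number of early deaths analysed. In the simulation, the estimated association between level and death was essentially untouched. This should be corrected before analysis. It does not by itself undermine the study's main question.

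**What to change.** 1. **Level.** Run Kaplan-Meier and Cox on baseline sUCR in all eligible patients, with time from baseline. One value is then enough, and level does not depend on how long a patient survives. Using a single value for early deaths and a follow-up mean for everyone else would not achieve this, because level would still be tied to survival.
2. **Change.** Compute mean sUCR and ΔsUCR in one prespecified early window. Start follow-up at the end of that window (a landmark), among patients still event-free with at least two values. A fixed window is needed: if the slope uses all visits, the visit that completes it is the last one, and entry there leaves almost no follow-up. Label the four-group plot as conditional on reaching the landmark.
3. **Reporting.** State whether the groups cross the two measures and whether Cox enters them jointly. Report the number and outcomes of patients who cannot be classified.

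The cost is some wording in the Statistics section and one extra set of curves from data already collected. Survival figures may be slightly less favourable, a single-value level is noisier than a mean, and the ΔsUCR analysis will contain fewer events.
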